6.1.1 Serious Adverse Events (SAE)

An AE should be classified as an SAE and reported as such, if it meets one or more of the following criteria:

- It results in death (i.e., the AE actually causes or leads to death)
- It is life threatening (i.e., the AE places the subject at immediate risk of death)
- It requires or prolongs inpatient hospitalization
- It results in persistent or significant disability/incapacity (i.e., the AE results in substantial disruption of the subject's ability to conduct normal life functions)
- It results in a congenital anomaly/birth defect in a neonate/infant born to a mother exposed to the investigational product
- It is considered a significant medical event by the investigator based on medical judgment (e.g., may jeopardize the subject or may require medical/surgical intervention to prevent one of the outcomes listed above)

If a subject is hospitalized to undergo a medical or surgical procedure as a result of an AE, the event responsible for the procedure, not the procedure itself, should be recorded as the event. For example, if a subject is hospitalized to undergo coronary bypass surgery, record the heart condition that necessitated the bypass.

Hospitalizations for the following reasons will not be recorded as SAEs:

- Hospitalization or prolonged hospitalization for diagnostic or elective surgical procedures for pre-existing conditions.
- Hospitalization or prolonged hospitalization required to allow outcome measurement for the study.
- Hospitalization or prolonged hospitalization for scheduled therapy of the target disease of the study.

6.1.2 Unanticipated Adverse Device Effects (UADE)

An unanticipated adverse device effect (UADE) is any serious adverse effect on health or safety or any life-threatening problem or death caused by or associated with a drug or device, if that effect, problem, or death was not previously identified in nature, severity or degree of incidence. Anticipated adverse events are identified in Section 6.3. UADEs also include any unanticipated sight-threatening events and any other unanticipated serious problem associated with a device that relates to the rights, safety, or welfare of subjects.

6.2 ADVERSE EVENT ASSESSMENT AND DOCUMENTATION

All subjects who have been exposed to the study treatment will be evaluated for adverse events. All adverse events, regardless of severity and whether or not they are ascribed to the study treatment, will be recorded in the source documents and CRF using standard medical terminology.

All adverse events will be evaluated beginning with onset, and evaluation will continue until resolution is noted, or until the investigator determines that the subject's condition is stable. The investigator will take appropriate and necessary therapeutic measures required for resolution of the adverse event. Any medication necessary for the treatment of an adverse event must be recorded on the concomitant medication case report form.

All AEs will be characterized by the following criteria:

- Date of onset
- Event diagnosis
- Intensity or severity
- Expectedness
- Relatedness to study treatment
- Treatment or action taken.
- Outcome

Whenever possible, recognized medical terms should be used when recording AEs. Colloquialisms and/or abbreviations should not be used. Only one medical concept, preferably a diagnosis instead of individual symptoms, should be recorded as the event.

If more than one distinct adverse event occurs, each event should be recorded separately. However, if known at the time of reporting, a diagnosis (i.e., disease or syndrome) should be recorded on the CRF rather than individual signs and symptoms. However, if a constellation of signs and/or symptoms cannot be medically characterized as a single diagnosis or syndrome at the time of reporting, each individual event should be recorded as a separate AE. A diagnosis that is subsequently established should be reported as follow-up information. However, signs and symptoms that are considered unrelated to an encountered syndrome or disease should be recorded as individual AEs.

Adverse events occurring secondary to other events (e.g., sequelae) should be identified by the primary cause; a "primary" event, if clearly identifiable, should represent the most accurate clinical term to record as the AE event term. For example:

Orthostatic hypotension ⇒fainting and fall to floor ⇒head trauma ⇒neck pain

The primary event is orthostatic hypotension and the sequelae are head trauma and neck pain.

6.2.1 Classification of Adverse Events by Intensity/Severity

All adverse events should be graded on a three-point scale (mild, moderate, severe) for intensity/severity, defined as a qualitative assessment of the level of discomfort of an adverse event as is determined by the Investigator or reported to him/her by the subject. The assessment

of intensity is made irrespective of study procedure relationship or seriousness of the event and should be evaluated according to the following scale:

- Mild:** Awareness of sign or symptom, but easily tolerated.
Moderate: Discomfort enough to cause interference with usual activity.
Severe: Incapacitating with inability to work or do usual activity.

There is a distinction between the severity and the seriousness of an adverse event. Severity is a measurement of intensity; thus, a severe reaction is not necessarily a serious adverse event (SAE). For example, a headache may be severe in intensity, but would not be serious unless it met one of the criteria for serious adverse events listed in Section 7.1.1.

6.2.2 Expectedness

All AEs will be evaluated as to whether they are expected or unexpected.

- Expected (anticipated):** An adverse event is expected when the nature, severity, or degree of incidence was previously described. Expected adverse events are listed in 7.3.
- Unexpected (unanticipated):** An adverse event is unexpected when the nature, severity, or degree of incidence was not previously described.

6.2.3 Relatedness

The study investigator will evaluate if the AE is related to the corneal cross-linking procedure. Relationship is defined in the following manner:

Not related: The event is **clearly related to other factors** such as subject's clinical state, therapeutic interventions, concomitant disease or therapy administered to the subject, and does not follow a known response pattern to the procedure.

Related: The event **follows a reasonable, temporal sequence from the time of procedure and/or follows a known response pattern to the study procedure and cannot be reasonably explained by other factors** such as subject's clinical state, therapeutic interventions, or concomitant therapy administered to the subject.

6.2.4 Treatment or Action Taken

Action taken in response to an adverse event will be recorded as:

- None
- OTC or Rx drug added
- Non-drug treatment/procedure
- Hospitalization or ER visit

Action taken with study procedure will be recorded as:

- None
- Study procedure interrupted
- Study procedure discontinued

6.2.5 Outcome

The clinical outcome of an AE will be characterized as follows:

- Resolved without sequelae
- Resolved with sequelae (specify)
- Ongoing (i.e. continuing at time of study discontinuation)
- Death
- Unknown.

6.3 ANTICIPATED ADVERSE EVENTS

Epithelial Defect – A breach in the corneal epithelium that does not heal within 24 hours.

Persistent Epithelial Defect - A breach in the corneal epithelium that does not heal within 2 weeks.

Significant Decrease in Visual Acuity – loss of ≥ 2 lines CDVA

Sterile Infiltrates – Gray-white lesions caused by acute immune response to corneal damage.

Central Stromal Scars – New, significant corneal opacity in the central stromal region.

Corneal Haze – Cloudy or opaque appearance of the cornea. Grade Scale: 0 = clear cornea; 1 = focal areas of minimal stromal clouding or reticulation; 2 = diffuse mild stromal clouding or reticulation; 3 = Diffuse stromal clouding or reticulation somewhat obscuring the iris details; 4 = focal or diffuse areas of dense stromal haze obscuring iris detail.

Infectious Keratitis – Microbial infection of the epithelium or stroma.

Corneal Melt – A progressive, rapidly expanding, erosive, non-infectious, corneal ulcer.

Non-Infectious Keratitis – Inflammation of the cornea not associated with an infection.

Eye Pain – Eye pain lasting for >5 days.

Conjunctiva Hyperemia – Eye redness.

Foreign Body Sensation – Patient reports a feeling of a foreign body (e.g. gravel or sand) in the eye lasting >24 hours.

Corneal Hydrops – Acute corneal edema caused by a break in Descement membrane.

Herpes Simplex Virus (HSV) Reactivation – Epithelial keratitis, stromal keratitis, or disciform edema proven or clinically diagnoses as being caused by HSV.

Disease progression – Increase of $\geq 4D K_{max}$ as assessed by topography or tomography or loss of > 2 lines of CDVA.

Photophobia – Sensitivity to light lasting > 24 hours.

Elevated Intraocular Pressure (IOP) – IOP ≥ 30 mmHg or an increase in IOP of ≥ 10 mm from baseline recorded on two separate occasions or an increase in IOP that requires intervention.

Dry Eye Syndrome (DES) – Irritation of corneal surface due to inadequate production of tears that is consistently worse than the patient's pre-procedure state longer than 3 months after the cross-linking procedure.

Endophthalmitis – Diffuse intraocular inflammation predominantly involving the vitreous cavity but also involving the anterior chamber, implying a suspected underlying infectious cause.

Iritis – Presence of inflammatory cells in the anterior chamber. The presence of aqueous flare alone is not considered to constitute iritis.

Iridocyclitis – Presence of inflammatory cells in both the aqueous and vitreous.

6.4 SERIOUS ADVERSE EVENT AND UNANTICIPATED ADVERSE DEVICE EFFECT REPORTING

Serious Adverse Events (SAE) and unanticipated adverse device effects (UADE) must be reported to the study sponsor (CXLUSA, LLC) and study Principal Investigator (PI) as soon as possible and no later than **24 hours** after the investigator first learns of the event.

For initial reports, investigators should record all case details that can be gathered within the reporting timeframe. The contact information for CXLUSA and the PI is below:

Study Sponsor:

CXLUSA, LLC

CONTACT PERSON: [name].
[name]
[name]
[contact]

Study Principal Investigator:

[name]., F.A.C.S.
ASSISTANT PROFESSOR OF CLINICAL OPHTHALMOLOGY
WASHINGTON UNIVERSITY SCHOOL OF MEDICINE
[name]
C/O OPHTHALMOLOGY ASSOCIATES
[name]
[name]
[contact]
[contact]

Relevant follow-up information should be submitted to the sponsor as soon as it becomes available and/or upon request. For some events, the sponsor or his designee may follow up with the site by telephone, fax, electronic mail, and/or a monitoring visit to obtain additional case details deemed necessary to appropriately evaluate the event (e.g., hospital discharge summary, consultant report, or autopsy report). Reports relating to the subject's subsequent medical course must be submitted to the study sponsor until the event has subsided or, in case of permanent impairment, until the event stabilizes and the overall clinical outcome has been ascertained.

7.0 STUDY DISCONTINUATION

The study sponsor has the right to terminate participation of an investigator, or this study, at any time. Reasons for termination may include, but are not limited to, the following:

- The incidence or severity of adverse events in this or other studies indicates a potential health hazard to subjects
- Subject enrollment is unsatisfactory
- Data recording is inaccurate or incomplete.
- Study has reached maximal enrollment.

8.0 STATISTICAL PLAN

Change from baseline will be calculated as follow-up visit – baseline. The baseline visit will be defined as Visit 1 (Pre-procedure visit). The required analyses and target endpoints include, but are not limited to those listed below. In general, continuous variables will be analyzed with two-sample t-tests for changes from baseline in normally distributed variables. For non-parametric data sets, Wilcoxon Signed Rank tests will be utilized. Patient demographics will be summarized using descriptive statistics (means, medians, standard deviations, etc.).

Subject demographic characteristics and background variables will be summarized. Treatment differences with respect to baseline characteristics will be discussed in the final study report and assessed.

All subjects enrolled in the study will be included as part of the safety analysis. All eyes treated (single or both eyes of an individual subject) will be included in the analysis of safety and efficacy.

To determine efficacy, standard statistical methods such as p value analyses of continuous variables will be used along with newer artificial intelligence algorithms such as *Logitboost* or *Random Forest* to detect groupings and correlations of various outcome variables.¹ Large data sets will be analyzed and in these analyses stratification by age, diagnosis, severity of disease, gender, tomography, topography metrics and other such criteria will be used to answer key questions related to the science and effects of treatments.

Reference: ¹*Statistical Learning for Biomedical Data* JD Malley, KG Malley, S Pajevic Cambridge University Press, 2011).

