3.4 STUDY POPULATION

Up to 3,000 subjects with asymmetric corneas will be enrolled. After providing informed consent and documenting it in writing, subjects with keratoconus, forme fruste keratoconus, post-LASIK ectasia, pellucid marginal degeneration, forme fruste pellucid marginal degeneration, diurnal fluctuation after RK, or Terrien's marginal degeneration will be screened for participation in the study. Screening evaluations may be performed at any time within 3 months preceding or on Day 0, and subjects must fulfill the following criteria:

Inclusion Criteria:

1. Diagnosis of keratoconus, forme fruste keratoconus, post-LASIK ectasia, pellucid marginal degeneration, forme fruste pellucid marginal degeneration, history of radial keratotomy with fluctuating vision, or Terrien's marginal degeneration.
2. Must have provided informed consent, documented it in writing, and have been given a copy of the signed informed consent form.
3. Must be willing and able to return for scheduled treatment and follow-up examinations for the duration of the study.
4. Must be at least 8 years of age.

Exclusion Criteria:

1. Corneal thickness < 375 microns measured by ultrasound or Pentacam.
2. Contraindications or sensitivities to any study medications or their components.
3. Pregnancy or breastfeeding.
4. Any history of herpes simplex corneal disease in an eye to be treated.
5. Nystagmus or any other condition that would, in the judgement of the investigator, prevent a steady gaze during the treatment.
6. Inability to cooperate with diagnostic tests.
7. Enrollment in another ophthalmic clinical trial.

Randomization:

Randomization will be stratified by indication and by investigational site, with study subjects randomly assigned to one of three treatment groups. The three treatment groups consist of CXLO Corneal Strengthening Solution combined with one of 3 different UVA exposure parameters. The UVA treatment parameters will consist of:

- Group 1: 4 mW/cm² cycled On/Off automatically at 15 second intervals for 20 minutes (total UVA corneal surface dose of 2.4 J/cm²),
- Group 2: 6 mW/cm² cycled On/Off automatically at 15 second intervals for 20 minutes (total UVA corneal surface dose of 3.6 J/cm²), and
- Group 3: 4 mW/cm² cycled On/Off automatically at 15 second intervals for 30 minutes (total UVA corneal surface dose of 3.6 J/cm²).

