4.0 STUDY TREATMENTS

4.1 INVESTIGATIONAL TREATMENT

One or both eligible eyes may be enrolled and procedure performed on the same day or on different days. Subjects eligible for enrollment will be instructed to instill Polytrim (or Floraquinolone or other appropriate broad spectrum antibiotic if the subject is hypersensitive) 4 times daily into the eligible eye(s) one day prior to treatment

- A. Instill anesthetic eye drops.
- B. Place a lid speculum in each eye undergoing treatment.
- C. Use a sterile ophthalmic sponge hydrated with saline or anesthetic drops to gently swab the surface of the cornea to remove mucus and any other debris and to enhance riboflavin penetration into the cornea. The epithelium is not to be removed, as treatment with an intact epithelium has the potential to halt progression of the disease while reducing post-procedure pain, complications related to epithelial debridement, and promoting faster vision recovery to baseline CDVA.
- D. Apply a sterile corneal sponge protector to the surface of the cornea to serve as a reservoir for CXLO Corneal Strengthening Solution.
- E. Saturate the sponge protector with several drops of CXLO Corneal Strengthening Solution. Thereafter, to assure for continuous application of CXLO solution to the surface of the cornea, keep the sponge moistened by applying 1-2 drops of CXLO solution every 1-3 minutes for 10-90 minutes (this range is required as different corneas load at different rates and the surgeon will visually confirm sufficient stromal loading later in the procedure).
- F. After 10-20 minutes of saturation, remove the lid speculum. Examine the eye using a slit lamp or slit light to confirm adequate saturation of the cornea, referencing the “flip-chart” of slit-lamp images, a copy of which is provided in Appendix 1. If the cornea is not adequately saturated, repeat the CXLO Corneal Strengthening Solution application instructions above,

and re-assess corneal saturation via slit-lamp or slit light examination every 5-10 minutes until adequate corneal stromal saturation is confirmed.

- G. After confirming adequate stromal saturation, irrigate the corneal epithelium with artificial tears for approximately 30 seconds prior to UVA illumination to avoid the “sunscreen” effect of riboflavin in the epithelium.
- H. Place the lid speculum(s) prior to UVA light application.

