- v. Over the counter oral analgesics such as ibuprofen, acetaminophen, or even narcotics may be taken for discomfort. Prescription pain meds such as acetaminophen with an opiate and/or a gabapentin modulator such as Lyrica may also be prescribed short term for patient comfort. Application of cold or ice packs may be recommended for improved comfort.

M. Punctal plugs can be placed at the surgeon's discretion if needed to improve the tear film.

Treating both eyes on the same day:

2 options:

1. Sequential epithelium preparation, sequential UVA light administration: Prepare epithelium in one eye, load the cornea with CXLO Corneal Strengthening Solution, then prepare the epithelium in the second eye prior to initiating the UV light source. While one eye is receiving UVA light therapy, the other eye is receiving the loading dose of topical CXLO solution.
2. Bilateral epithelium preparation, simultaneous UV light treatment: Prepare epithelium in both eyes, and initiate CXLO solution drops in both eyes. After 10-90 minutes of loading both eyes with riboflavin, the eyes will be checked with a slit lamp or slit beam check. UV light treatment in both eyes will then be performed.

Post-Procedure Treatment Regimen Details:

Topical corticosteroids and antibiotics as per standard surgeon regimen following other UV procedures such as PRK may be used. Topical nonsteroidal medications and dilute anesthetic drops may be used as needed for early postop discomfort, but should be discontinued by post-procedure day 6.

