8.1 EFFICACY ENDPOINTS

The primary efficacy endpoint of this trial is change in corrected distance visual acuity (CDVA) at the last required study visit (6 months post-op), compared to baseline. CDVA will be evaluated by an observer who is masked to the treatment protocol to which study subjects have been assigned. All eyes treated (single or both eyes of an individual subject) will be included in the analysis of efficacy.

The Secondary Endpoints will be:

1. Change in UCVA at 6 months, compared to baseline.
2. Change in K_{\max} , compared to baseline.

Additional analyses will be performed in subgroups of patients using standard statistical stratification methods, including patients over the age of 35, patients under the age of 18, disease severity, and patients with and without pre-procedure corneal scars. Results in male vs. female patients and post LASIK ectasia vs. primary keratoconus will also be evaluated.

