8.2 SAMPLE SIZE JUSTIFICATION

Three thousand subjects will be enrolled in this open-label, prospective multicenter trial. One or both eyes of each patient may be enrolled and evaluated, based on whether treatment is unilateral or bilateral, based on clinical indications. All eyes treated (single or both eyes of an individual subject) will be included in the analysis of safety and efficacy.

A substantial number of eyes will need to be treated and evaluated in this study in order to obtain sufficient data to facilitate the analysis of potential differences between and among patient groups for each study indication. For example, it is expected that presenting disease severity, prior treatment (e.g. Intacs), subject age, and corneal thickness will impact the magnitude of effect of procedure efficacy for the treatment of keratoconus, forme fruste keratoconus, post-LASIK ectasia, pellucid marginal degeneration, and forme fruste pellucid marginal degeneration. Accordingly, in order to perform analyses with adequate study power, a large sample size is required.

A large sample size for a study involving fewer but similar indications is not unprecedented, as FDA clearance was previously granted for the conduct of a clinical study involving only keratoconus and post-LASIK ectasia (ref: <http://clinicaltrials.gov/ct2/show/NCT01459679>). Although that study was a Phase 3 clinical trial, it is expected that the study power needed to support analyses and conclusions of this proposed CXXLUSA study will be similar and further justifies the proposed sample size.

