12. If simultaneous, bilateral corneal cross-linking will be performed, turn the selector switch on the front of the Power Control Box to “Dual”. Note that the LED on top of the control box is illuminated.
13. Repeat calibration steps above to calibrate the right UVA emission aperture.
14. After completion of calibration procedures, re-swipe the Calibration card to close the illumination source shutter.
15. Ensure the patient is lying down in a comfortable position. Provide a pillow for their back or neck if needed to ensure comfort and reduce movement during the treatment. Instruct the patient to remain in this position without moving their head and, when necessary, repeat these instructions to avoid movement during the procedure.
16. For treatment, position the UVA optic at the distance from the cornea that was previously measured to create a 12 mm diameter circle. This consistently provides a 12 mm UVA beam spot size.
17. Swipe a Treatment card labeled with the Randomization Group to which the patient has been randomized.
18. Center the beam on the cornea. This is easily performed since the UVA beam spot size is easily delineated by bright fluorescence of the riboflavin-loaded cornea, assuring for easy and consistent beam centration. Use this fluorescence and easy visibility of the beam to confirm accurate positioning at the initiation UVA illumination, and throughout the Treatment procedure.

If the patient moves, you will see the beam is off center. The image below shows a decentered beam that can be seen to not sufficiently cover the cornea (right yellow arrow) and to be decentered onto the eyelid (left yellow arrow). During the UV procedure, the centration is monitored in this fashion in each eye. In this image, no speculum has been placed. In the current study, speculae will be placed which will also assist in centration and placement of the UVA beam making these even more accurate and safer.

Beam Properly Centered

Beam Off Center

19. Monitor the patient's cooperation and eye position during the dark cycle of treatment i.e. when the UVA light has been turned off by the illumination source shutter. If the patient tends to look away from the optic, this is obvious and the patient should be instructed to look straight ahead again.

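### The protocol's 6-month CDVA analysis uses every treated eye but names only tests that assume independent observations, although eyes treated together share the subject's randomised arm

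*Protocol*

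**What the plan says.** Protocol 8.0 names the tests: "In general, continuous variables will be analyzed with two-sample t-tests for changes from baseline in normally distributed variables". It adds: "For non-parametric data sets, Wilcoxon Signed Rank tests will be utilized". Protocol 8.1 makes 6-month change in CDVA from baseline the primary endpoint and sets the unit of analysis: "All eyes treated (single or both eyes of an individual subject) will be included in the analysis of efficacy". The Statistical Methods entry of the Protocol 1.0 summary repeats the tests and the all-eyes rule. Protocol 8.2 repeats the all-eyes rule and explains: "One or both eyes of each patient may be enrolled and evaluated, based on whether treatment is unilateral or bilateral".

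Allocation is by subject. Protocol 3.4 describes randomisation "with study subjects randomly assigned to one of three treatment groups". Appendix 3, step 17, ties the illumination to the person: "Swipe a Treatment card labeled with the Randomization Group to which the patient has been randomized". Section 4.1 allows two eyes per subject: "One or both eligible eyes may be enrolled and procedure performed on the same day or on different days". One of its two same-day options is "Bilateral epithelium preparation, simultaneous UV light treatment".

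SAP 2.3 records that eyes treated together initially sit under one patient number. A fellow eye treated later, or a repeat course, gets a new number, and subsequent treatment is re-randomised. Sites are to supply a list that links the numbers belonging to one person.

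The SAP's efficacy analysis works differently from the protocol's. It uses one primary eye (3.7), a separate fellow-eye analysis and ANOVA across the three arms (5.1).

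**The concern.** Two eyes of one person, treated together with the same UVA parameters, do not carry the information of two independent observations. The two-sample t-test and the signed-rank test both count them as if they did. No protocol section mentions correlation between fellow eyes, clustering, GEE or a mixed model.

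At stake is inference on the primary endpoint. Differences between UVA arms, and improvement within an arm, would reach nominal significance too often. SAP section 1 says that data from this study will support the Phase 3 design, so overstated precision could carry forward.

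A secondary gap concerns non-normal data. The signed-rank test addresses change within one arm and cannot compare three independent arms. Neither document names a rank test that does.

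**Working it through.** **No planned figure to reproduce.** Protocol 8.2 gives 3,000 subjects without an effect size, SD, significance level or power.

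**Inputs.** The documents supply the unit of analysis, the tests, subject-level allocation to three arms, and re-randomisation of later treatment. The following are assumptions:
- a two-sided 5% level and 1:1:1 allocation;
- *b*, the share of persons with both eyes treated: 0.25 to 0.5;
- *s*, the share of those pairs treated together in one arm, the rest being re-randomised: 0 to 1;
- *r*, the between-eye correlation of change: 0.3 to 0.7.

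**Formulas.** These give the true variance divided by the variance assumed under independence.
- Arm contrast: 1 + 2*rbs*/(1+*b*). Re-randomised pairs drop out, because those landing in the same arm and those split across the contrasted arms cancel in expectation.
- Within-arm change: 1 + 2*rb*[*s* + (1−*s*)/3]/(1+*b*). One third of re-randomised pairs still share an arm.
- True error: 2[1 − Φ(1.96/√ratio)].

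**Lead case** (*b* = 0.5, *s* = 0.5)
- Contrast, *r* = 0.3: 1 + 2(0.3)(0.5)(0.5)/1.5 = 1.10, error 6.2%. At *r* = 0.7 the ratio is 1.233 and the error 7.8%.
- Within arm, *r* = 0.3: 1 + 2(0.3)(0.5)(0.667)/1.5 = 1.133, error 6.6%. At *r* = 0.7 the ratio is 1.311 and the error 8.7%.

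| *b*, *s* | Contrast error, *r* = 0.3 / 0.5 / 0.7 | Within-arm error, *r* = 0.3 / 0.5 / 0.7 |
|---|---|---|
| 0.5, 0.5 | 6.2 / 7.0 / 7.8% | 6.6 / 7.6 / 8.7% |
| 0.25, 0.5 | 5.7 / 6.2 / 6.6% | 5.9 / 6.6 / 7.2% |
| 0.5, 1 | 7.4 / 9.0 / 10.6% | 7.4 / 9.0 / 10.6% |
| 0.5, 0 | 5.0 / 5.0 / 5.0% | 5.8 / 6.3 / 6.8% |

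**Simulation** (900 persons, three arms, 20,000 runs), lead case. The all-eyes t-test between arms rejected in 6.2, 7.0 and 7.9% of runs. The all-eyes signed-rank test within an arm rejected in 6.6, 7.4 and 8.3%. A person-clustered test stayed at 4.3 to 5.6% across the simulated cases (4,000 runs).

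**Repeat courses.** With 5 to 20% of eyes re-entered and re-randomised, arm contrasts stayed at 4.5 to 5.3% and within-arm signed-rank at 4.9 to 5.8%. They are not the source of the inflation.

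**Signed-rank test.** With two arms given the same mean change of −0.05 (SD 0.2, 300 per arm, all assumed), the test within an arm rejects in 99% of runs. It detects change over time and says nothing about a difference between arms.

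**Would the SAP's worse-eye rule be a remedy?** SAP 3.7 selects, in bilateral cases, the eye with the lower baseline CDVA. Selecting on baseline brings regression to the mean into change from baseline. With no true change, signed-rank on the worse eye rejected in 6 to 45% of simulated runs (assumed: 300 persons per arm, 25 to 50% bilateral, between-subject SD 0.2 logMAR, measurement SD 0.05 to 0.10, between-eye acuity correlation 0.3 to 0.7). A second set of runs gave 8 to 65%. For within-arm change this can be worse than the fault it would cure.

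**The case against.** The strongest reply is that the SAP already deals with this. It analyses one eye at a time, replaces t-tests by ANOVA because there are three arms, includes Month 6, and says that its language governs where it conflicts with the protocol. For the interim analysis that stands, and a reader should not infer that the interim results are affected. But SAP section 1 limits this version to the analyses supporting the FDA meeting. Efficacy is restricted to keratoconus (3.2.3), no hypotheses are tested (3.2.3.1), and the primary measure is at Month 12 (5.1). It supplies no method for the protocol's 6-month analysis across all indications.

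Second, Protocol 8.0 uses permissive wording: its tests apply in general, and its list of analyses is not exhaustive. A clustered analysis is therefore not excluded. That stands too, but permitting a method is not specifying it.

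Third, this is an open-label Phase 2 trial with no declared significance level, and every input to the size of the effect is assumed. That limits the claim to direction plus a conditional size.

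Two stronger readings are tempting. One is that planned confidence intervals are too narrow: the protocol's statistical sections plan none, and the SAP's intervals use one eye per subject. The other is that arm contrasts must be inflated: they are not if all second eyes are re-randomised.

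Finally, the SAP rests on protocol version 4.3, which was not supplied. SAP 1.4 and 1.6 suggest that the all-eyes and t-test sentences survive there. The signed-rank sentence cannot be confirmed.

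**Conclusion.** The point holds for the protocol's own analysis. Followed as written, Protocol 8.0 and 8.1 give standard errors and p-values that are too favourable whenever eyes in the same arm are positively correlated. The direction follows from the design; the size rests on the assumptions listed above. It is moderate in the lead case, reaches 10.6% if half of subjects are bilateral, all pairs share an arm and the correlation is 0.7, and is absent for arm contrasts if no pair is treated together. It should be settled before the final analysis. The missing between-arm rank test is secondary: it matters only if data are judged non-normal, and only if the sentence remains in version 4.3.

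**What to change.** First check version 4.3. Then, in Protocol 8.0/8.1 and the matching summary text, or in the final SAP:

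- Analyse 6-month CDVA change on all first-course treated eyes with a linear mixed model, or GEE with robust errors, with UVA arm as a three-level factor. Use it for both arm contrasts and within-arm change.
- Cluster on the person, linked through the SAP 2.3 number map, since patient number does not identify a person. Report repeat courses separately.
- If a rank analysis is needed, compare arms by Kruskal-Wallis with pairwise rank-sum tests on one eye per person, or by a clustered rank test.
- Do not use the SAP 3.7 worse-eye rule for within-arm change from baseline. It may serve as a supportive between-arm analysis.

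The change is to wording and needs no new trial data; the SAP already provides for the number map. The cost is wider, more honest uncertainty. In the lead case the standard error of an arm contrast rises by 5 to 11% (√1.10 = 1.05 to √1.233 = 1.11), and across the simulated cases by 0 to 21%. Using one eye per person costs more, 12 to 23%.
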